**The amendment also includes several other minor clarifications and corrections:**

- Medical monitor contact information and Celgene therapeutic head signature page were updated on pages 2 and 3.

- Citations of AG-221 and azacitidine IBs were removed in Section 17 and the links to these citations (in the Protocol Summary, and Sections [redacted] 10.6) were abolished to allow reference to the current IBs.

- Multi-gated acquisition (MUGA) scan was removed as an assessment during screening and/or treatment. However, a prior MUGA scan performed within 28 days prior to the start of study treatment can be used for study entry. These changes were reflected in the Protocol Summary, Table 3, and Sections 6.1, 6.2, and 6.4.
- The window for bone marrow aspirate and/or biopsy, peripheral blood smear and, if applicable, cytogenetics, during the Treatment Phase was clarified in the footnotes “w”, “x” and “y” of Table 3 to be consistent with Section 6.2.
- The window for bone marrow aspirate and/or biopsy, peripheral blood smear and, if applicable, cytogenetics, during the Follow-up Phase was corrected in Section 6.3 to  $\pm 14$  days to be consistent with the footnote “q” of the Protocol, Table 3, Table of Events.
- The parameters of chemistry and cardiac marker panels were updated.
- Truncated sentences in Sections 8.1 and 10.6 were completed.
- The elapsed time from azacitidine reconstitution to administration in Method A of Appendix K was updated with addition of the specification in the United States.
- Specification of azacitidine reconstitution with refrigerated water was added in Method B of Appendix K.
- Corrections of minor typographical errors and incidental formatting changes were made throughout the document.

1. LIST OF ABBREVIATIONS

Table 1: Abbreviations and Specialist Terms

Abbreviation or Specialist Term	Explanation
ADaM	Analysis Data Model
ADT	Analysis Date
AE	Adverse event
ALT	Alanine aminotransferase (SGPT)
AML	Acute myeloid leukemia
ANC	Absolute Neutrophil Count
AST	Aspartate aminotransferase (SGOT)
ATC	Anatomical therapeutic chemical
BID	Twice a day
BMI	Body mass index
BSA	Body surface area
BSC	Best supportive care
BPM	Beats per minute
CCR	Conventional care regimen
CI	Confidence interval
CR	Morphologic complete remission
CRc	Cytogenetic Complete Remission
CRF	Case report form
CRh	Morphologic complete remission with partial hematologic recovery
CRi	Morphologic complete remission with incomplete neutrophil recovery
CRp	Morphologic complete remission with incomplete platelet recovery
CTCAE	Common Terminology Criteria for Adverse Events
DMC	Data Monitoring Committee
ECG	Electrocardiogram
ECOG	Eastern Cooperative Oncology Group
eCRF	Electronic case report form
EFS	Event-free survival
EORTC	European Organization for Research and Treatment of Cancer

Abbreviation or Specialist Term	Explanation
EOT	End of treatment
FCBP	Females of childbearing potential
HI	Hematologic improvement
HI-E	Hematologic improvement erythroid response
HI-N	Hematologic improvement neutrophil response
HI-P	Hematologic improvement platelet response
HLT	High-Level Term
HSCT	Hematopoietic stem cell transplantation
IDAC	Intermediate-dose cytarabine
IDH2	Isocitrate dehydrogenase isoform 2
IRAC	Independent Response Assessment Committee
ITT	Intent-to-treat
IV	Intravenous
IVRS	Interactive voice response system
IWG	International Working Group
KM	Kaplan-Meier
MedDRA	Medical dictionary for regulatory activities
MLFS	Morphologic leukemia-free state
NCI	National Cancer Institute
ORR	Overall response rate
OS	Overall survival
PR	Partial remission; same as partial response
PD	Progressive disease
QTcB	Heart-rate corrected QT with Bazett's correction
QTcF	Heart-rate corrected QT with Fridericia's correction
SAE	Serious adverse event
SD	Stable disease
SGPT	Serum glutamic pyruvic transaminase
SMQ	Standardized MedDRA Query

Abbreviation or Specialist Term	Explanation
SOC	System organ class
TEAE	Treatment emergent adverse event
ULN	Upper limit of normal

2. INTRODUCTION

This statistical analysis plan (SAP) describes the analyses and data presentations for Celgene's protocol AG-221-AML-004 "A Phase 3, Multicenter, Open-label, Randomized Study Comparing the Efficacy and Safety of AG-221 (CC-90007) Versus Conventional Care Regimens (CCR) in Older Subjects with Late Stage Acute Myeloid Leukemia Harboring an Isocitrate Dehydrogenase 2 Mutation," which was issued on 13 Aug 2015 and amended to Amendment 2.0 on 30 Nov 2017. It contains definitions of analysis populations, derived key efficacy variables, and statistical methods for the analysis of efficacy and safety data.

The efficacy analyses include one interim analysis and one final analysis. Throughout this SAP, the treatment arms will be referred to as AG-221 and CCRs (Conventional Care Regimens). Treatment arm AG-221 refers to AG-221 Orally (PO) plus best supportive care (BSC). The CCR treatment options include BSC only, azacitidine subcutaneously (SC) plus BSC, low-dose cytarabine (LDAC) SC plus BSC, or intermediate-dose cytarabine (IDAC) intravenously (IV) plus BSC. Following review of eligibility, subjects will be assigned by the investigator to one of the CCR treatment options based on the investigator's assessment of subjects' eligibility. Following the selection of a CCR treatment option, subjects will be randomized centrally in a 1:1 ratio to receive either the AG-221 treatment or the CCR treatment option pre-selected by the investigator.

A planned interim analysis was completed in March 2019, following the reporting of 65% of the expected number of deaths (approximately 163 deaths). Following this the study was continued to final analysis. This SAP provides a comprehensive and detailed description of the strategy, rationale, and statistical techniques to evaluate the efficacy and safety endpoints. The purpose of the SAP is to ensure the credibility of the study findings by pre-specifying the statistical approaches to the primary efficacy analysis of study data prior to database lock for the final analysis. A data cut-off date for the locked database for the final analysis will be determined and the database will be locked after medical/scientific review of the data has been completed, protocol violations/deviations have been identified, and the data have been declared to be clean. All statistical analyses detailed in this SAP will be conducted using SAS[®] Version 9.2 or higher.

The analysis methods and timing of analysis for the patient reported outcomes/quality of life [REDACTED] will be described in a separate pharmacoeconomics SAP. [REDACTED]

[REDACTED] Operational details for the Data Monitoring Committee (DMC) during the course of the study will be discussed in a separate DMC charter, and will not be included in this SAP either.

3. STUDY OBJECTIVES

3.1. Primary Objective

- To determine the primary efficacy, measured as overall survival (OS), of AG-221 compared with CCRs in subjects 60 years or older with acute myeloid leukemia (AML) refractory to or relapsed after second- or third-line AML therapy and positive for an isocitrate dehydrogenase isoform 2 (IDH2) mutation

3.2. Secondary Objectives

- To determine the supporting efficacy of AG-221 compared with CCRs
- To determine the safety and tolerability of AG-221 compared with CCRs
- To determine the effect of AG-221 compared with CCRs on Health-related Quality-of-Life (HRQoL)

4. INVESTIGATIONAL PLAN

4.1. Overall Study Design and Plan

This is an international, multicenter, open-label, randomized, Phase 3 study comparing the efficacy and safety of AG-221 versus CCRs in subjects 60 years or older with AML refractory to or relapsed after second- or third-line AML therapy and positive for an IDH2 mutation.

It is planned that approximately 316 subjects will be randomized in a 1:1 ratio to receive either the AG-221 treatment or the CCR treatment option pre-selected by the Investigator prior to randomization. Randomization will be stratified by prior intensive therapy for AML (yes versus no), primary refractory (i.e., morphologic complete remission [CR], CR with incomplete neutrophil recovery [CRi], or CR with incomplete platelet recovery [CRp] has never been attained) (yes versus no), and prior allogeneic hematopoietic stem cell transplantation (HSCT) for AML (yes versus no).

The treatment options in the CCR treatment arm include:

- BSC only: continuous 28-day cycles of BSC. Best supportive care includes, but is not limited to, hydroxyurea for leukocytosis and/or differentiation-like syndrome, anti-infectives, analgesics, antiemetics, antipyretics, transfusions and nutritional support (refer to [protocol Section 8](#) for details);
- Azacitidine SC plus BSC: continuous 28-day cycles of azacitidine 75 mg/m²/day SC for 7 days, plus BSC;
- LDAC SC plus BSC: continuous 28-day cycles of cytarabine 20 mg SC twice a day (BID) for 10 days, plus BSC;
- IDAC IV plus BSC: 28-day cycles of cytarabine 0.5 to 1.5 g/m²/day IV for 3 to 6 days, per standard institutional practice, plus BSC; only BSC given after IDAC therapy concludes per standard institutional practice.

Subjects randomized to the AG-221 treatment arm will receive AG-221 100 mg PO once a day on Days 1 to 28 of each 28-day cycle, plus BSC. Dose escalation to 200 mg may occur for augmenting treatment response.

Study treatment starts within 3 days after randomization. No crossover between any of the treatment options will be permitted during the course of study treatment per protocol.

Dosing interruptions, delays, or dose modifications may occur for managing toxicities and/or augmenting treatment response during study treatment.

[figure not shown]
All subjects who have received at least one dose of study treatment should undergo end-of-treatment (EOT) evaluations when study treatment is discontinued. The reason for discontinuation will be recorded in the electronic case report form (eCRF) pages and in the source document.

All subjects discontinued from study treatment for any reason other than withdrawal of consent for follow-up will continue to be assessed for adverse events (AEs), concomitant medications,

concomitant procedures, transfusions, [REDACTED] response, hematologic improvement (HI), subsequent AML therapies, and survival.

The study schematic is presented in Figure 1 below.

Figure 1: Overall Study Design

Key: AML = acute myeloid leukemia; BSC = best supportive care; CCR = conventional care regimen; HSCT = hematopoietic stem cell transplantation; IDAC = Intermediate-dose cytarabine; IDH2 = isocitrate dehydrogenase isoform 2; IV = intravenously; LDAC = low-dose cytarabine; PD = progressive disease; PO = orally; SC = subcutaneously.

* Stratification factors: prior intensive therapy for AML (yes versus no), primary refractory (yes versus no), and prior allogeneic HSCT for AML (yes versus no).

4.2. Study Endpoints

4.2.1. Primary Endpoint

The primary endpoint is overall survival (OS), defined as time from randomization to death due to any cause.

4.2.2. Secondary Endpoints

The secondary endpoints are listed in Table 2 below.

Table 2: Secondary Endpoints

Name	Description
Overall response rate	Rate of Best Response in CR + CRi + CRp + PR + MLFS according to modified IWG AML response criteria
Event-free survival	Time from randomization to documented morphologic relapse, PD according to modified IWG AML response criteria or death from any cause, whichever occurs first
Duration of response	Time from the first documented CR/CRi/CRp/PR/MLFS to documented morphologic relapse, PD according to modified IWG AML response criteria or death due to any cause, whichever occurs first
Time to response	Time from randomization to first documented CR/CRi/CRp/PR/MLFS according to modified IWG AML response criteria
Time to best response	Time from randomization to the documented best response of CR/CRi/CRp/PR/MLFS according to modified IWG AML response criteria
Treatment mortality at 30- and 60-day	Rate of death from any cause within 30 and 60 days of initiation of study treatment
One-year survival	The probability of survival at 1 year from randomization
Overall remission rate	Rate of CR + CRi + CRp according to modified IWG AML response criteria

Name	Description
Complete remission rate	Rate of CR according to modified IWG AML response criteria
Hematologic improvement rate	Rate of HI-N + HI-P + HI-E according to IWG MDS HI criteria
Rate of HSCT	Rate of bridge-to-HSCT through study treatment
Time to treatment failure	Time from randomization to discontinuation of study treatment due to any cause
Rate of CR/CRh	Rate of CR + CRh (Appendix 15.5)
Duration of CR/CRh	Time from the first documented CR/CRh to relapse according to modified IWG AML response criteria or death due to any cause, whichever occurs first
Time to CR/CRh	Time from randomization to first documented CR/CRh
Safety and tolerability	Type, frequency, severity, seriousness and relationship of adverse events to study treatments; vital signs; ECG; clinical laboratory evaluations
HRQoL	European Organization for Research and Treatment of Cancer Quality-of-Life questionnaire (EORTC QLQ-C30) and EuroQoL Group EQ-5D-5L instrument

Abbreviations: AML = acute myeloid leukemia; CR = morphologic complete remission; CRi = morphologic complete remission with incomplete neutrophil recovery; CRp = morphologic complete remission with incomplete platelet recovery; CRh=morphologic complete remission with partial hematologic recovery; ECG = electrocardiogram; EORTC= European Organization for Research and Treatment of Cancer; HI = hematologic improvement; HI-E = hematologic improvement erythroid response; HI-N = hematologic improvement neutrophil response; HI-P = hematologic improvement platelet response; HRQoL = Health-related Quality of Life; HSCT = hematopoietic stem cell transplantation; IWG = International Working Group; MDS = myelodysplastic syndromes; MLFS = morphologic leukemia-free state; PR = partial remission; PD = progressive disease.

4.2.4. Safety Endpoints

Safety assessments include physical examination, vital signs, electrocardiogram (ECG), hematology, serum chemistry, cardiac markers, fasting lipid panel, pregnancy testing (for females of childbearing potential [FCBPs] only), AEs, concomitant medications, concomitant procedures and transfusions. After screening, echocardiogram (ECHO), urinalysis and coagulation will be repeated as clinically indicated.

4.3. Stratification, Randomization, and Blinding

Randomization will be carried out using an Interactive Voice Response System (IVRS). Following the selection of a CCR treatment option, subjects will be randomized centrally in a 1:1 ratio to receive either AG-221 treatment or one of the CCR treatment options pre-selected by the Investigator based on standard institutional practice and on evaluation of the subject's underlying disease condition. To avoid potential bias, the intended treatment selection from the CCR treatment arm by the Investigator will be recorded for all subjects prior to randomization; treatment assignment is not to be subsequently changed after randomization.

To further minimize the heterogeneity of treatment modalities and clinical outcomes in AML, randomization in this study is stratified by the following three factors that are believed to have the most impact to the study's primary endpoint, OS: prior intensive therapy for AML (yes versus no), primary refractory (i.e., CR/CRi/CRp has never been attained) (yes versus no), and prior allogeneic HSCT for AML (yes versus no).

Although this is an open-label study, the interim efficacy analysis will be performed by an independent third party and results will be kept strictly confidential in order to maintain the integrity of the study. The study team will be blinded at summary-level information using actual treatment, i.e. no summary tables and figures will be produced or reviewed by the study team using actual treatment information. An independent unblinded team will produce the unblinded

results and send to an independent Data Monitoring Committee (DMC) who will review and give advice to the Sponsor regarding the study conduct.

4.4. Sample Size Determination

The equality of OS curves will be compared between the AG-221 and combined CCR treatment arms using a stratified log-rank test. Subjects will be randomized to receive AG-221 treatment or a CCR treatment option pre-selected by the Investigator in a 1:1 ratio. Assuming a median OS of 5.6 months in the CCR treatment arm, a median OS of 8 months in the AG 221 treatment arm (42.9% improvement), and a drop-out rate of approximately 9%, this design requires 316 subjects (158 per treatment arm) to be randomized, and 250 deaths to be observed in order to achieve 80% power to detect a hazard ratio (HR) of 0.7 and demonstrate a statistically significant difference in OS at type I error rate of 0.05 (two-sided). It is assumed that the OS distribution is exponential with a constant failure rate and that accrual rate is 3 subjects per month for the first 12 months and 9 subjects per month afterwards. The interim analysis for superiority will be conducted at 65% information (i.e., approximately 163 deaths) based on Lan-DeMets version of the O'Brien-Fleming alpha spending function (DeMets and Lan, 2008)

5. GENERAL STATISTICAL CONSIDERATIONS

5.1. Reporting Conventions

The following reporting conventions apply generally to tables, listings, and figures:

- Data from all study centers will be combined for analysis;
- Efficacy and Safety analyses will be done by treatment groups/options (AG-221 versus CCR overall and furthermore AG-221 versus, BSC Only, Azacitidine + BSC, LDAC + BSC, and IDAC + BSC by pre-selected CCR group). Exceptions will be noted in corresponding sections;
- All stratified efficacy analyses will use the randomization stratification factors taken from CRF (primary) including prior intensive therapy for AML (yes versus no), primary refractory (yes versus no), and prior allogeneic HSCT for AML (yes versus no) and repeated for stratification factors taken from IVRS.
- In stratified analysis, if stratified model does not converge due to small sample size, the stratification factor leads to least subjects will be dropped from the model. If a stratification factor has less than 40 subjects in one of its two levels across treatment groups, then this factor will not be used in stratified analysis;
- All statistical tests of the treatment effect will preserve a significance level of 0.05 for two-sided tests, unless otherwise specified;
- P-values will be rounded to 4 decimal places. P-values that round to 0.0000 will be presented as '<0.0001' and p-values that round to 1.000 will be presented as '>0.9999';
- Confidence intervals (CIs) will be presented as two-sided 95% CIs unless specified differently in specific analysis;
- Summary statistics will consist of the number and percentage of subjects (or cycles, if appropriate) in each category for discrete variables, and the sample size, mean, median, standard deviation, minimum, and maximum for continuous variables;
- All mean and median values will be formatted to one more decimal place than the measured value. Standard deviation values will be formatted to two more decimal places than the measured value;
- All percentages will be rounded to one decimal place. The number and percentage of responses will be presented in the form XX (XX.X%), where the percentage is in the parentheses;
- All listings will be sorted for presentation in order of treatment group, study center, subject, and date/time of procedure or event. Subjects who are screened but not randomized will be listed separately as a non-randomized group;
- All analysis and summary tables will have the analysis population sample size (i.e., number of subjects);

- The day of the first dose of any study drug will be defined as Day 1; for BSC only subjects, Day 1 is the randomization day.
- Unless noted otherwise, baseline value will be defined as the last non-missing value prior to or on the start of study treatment on Day 1 of Cycle 1. For subjects in the BSC only group, the baseline value will be defined as the last non-missing value on or prior to date of randomization. For subjects who are randomized but not treated, the baseline will be the assessment value on or prior to randomization date.
- To summarize efficacy/safety data by visit, the post-baseline results will be summarized by the scheduled visit or the derived visit as appropriate.
- In general, the derived visit is the same as the scheduled visit in the protocol which is defined by study day; data that is closest to derived visit (before and after) will be used as the value for that visit. In case that two data collected at the equal distance to the derived visit, the later one will be used.
- Calculation of Cycles:

The start date of each treatment cycle will be calculated based on study drug exposure records for each subject, except for BSC only subjects. The start date of the first cycle will be the earliest date the subject receives any study drug or the date of randomization for subjects receiving BSC only. Once the start dates, e.g., $S_1, S_2, S_3 \dots$ are calculated, the end date of each cycle is calculated as the day before the start date of the following cycle, i.e., $E_i = S_{i+1} - 1$. For subjects receiving BSC only, each cycle has a defined length of 28 days; for the last cycle, the end date will be calculated as the date of discontinuation from the treatment period. The cycle number for each date of interest, e.g., adverse event (AE) will be calculated based on event start date and the cycle window start and end dates. If an event date is on or after S_i and before S_{i+1} , the corresponding cycle number will be i .

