d The subject should start study treatment (ie, Day 1 of Cycle 1) within 3 days after randomization.

e Subject should continue to be eligible for study entry prior to the start of study treatment on Day 1 of Cycle 1.

- f Cycle 1 only.
- g See Section 6.1 for details regarding collecting BMA, BMB, PBS and cytogenetics at screening for assessing AML disease status, collecting BMA and PB at screening for central testing IDH gene mutations [REDACTED]. In the event that the central laboratory result is delayed and precludes acute clinical management of a subject who has confirmed IDH2 gene mutation by local evaluation, the subject may be eligible for randomization with approval by the Medical Monitor.
- h All prior medications (prescription and non-prescription) taken and treatment procedures received from the 4-week period (ie, 28 days) prior to starting study treatment (including those prior to the start of study treatment on Day 1 of Cycle 1), and all prior anticancer therapies, regardless of discontinuation date of treatment.
- i Documentation of CCR treatment option selected by the investigator must occur prior to randomization.
- j Source documented only.
- k The BSA calculation is per the Dubois & Dubois formula:  $BSA (m^2) = \text{weight (kg)}^{0.425} \times \text{height (cm)}^{0.725} / 139.2$ . Where applicable, the dose should be calculated on Day 1 of each treatment cycle.
- l These assessments will be done locally.
- m The screening ECHO does not need to be repeated if a prior ECHO or multi-gated acquisition (MUGA) scan has been performed within 28 days prior to the start of study treatment.
- n Pregnancy test is required for all FCBPs (see Section 4.2 for the definition). Serum  $\beta$ -hCG pregnancy test (sensitivity of at least 25 mIU/mL) will be performed centrally at screening. For FCBP subjects, a local serum or urine (investigator's discretion under local regulations)  $\beta$ -hCG pregnancy test (sensitivity of at least 25 mIU/mL) is to be done within 72 hours prior to study treatment administration on Day 1 of every treatment cycle in the Treatment Phase and at the EOT visit. Negative results are required for study treatment administration.

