### 6.1. Screening Phase

Screening evaluations start from ICF signing and must be completed within 28 days prior to the start of study treatment, unless noted otherwise below. Screening laboratory values must demonstrate subject eligibility, but may be repeated within the screening window, if necessary.

The following will be performed at screening as specified in the Table of Events, [Table 3](#), after written ICFs have been obtained:

- Registration of screening in IVRS
- Inclusion and exclusion criteria
- Demographics (age, sex, race, and ethnicity)
- Information supporting the initial diagnosis of AML by local pathology and cytogenetics review, including reports of bone marrow aspirate and/or biopsy, peripheral blood smear, cytogenetics and other tests if pertinent
- Prior AML therapies including surgery, radiation, systemic or any other therapy for the subject's AML disease, particularly induction/re-induction/salvage chemotherapies, consolidation or maintenance therapies, HSCT, low-intensity AML therapies such as azacitidine, decitabine or LDAC, or other medications considered supportive care for AML, regardless of discontinuation date of treatment
- Information supporting CR/CRi/CRp attained during prior AML therapies by local pathology and cytogenetics review, including reports of bone marrow aspirate and/or biopsy, peripheral blood smear, cytogenetics, and other pertinent tests
- AML disease status at screening determined by local pathology and cytogenetics review and confirmed retrospectively by central review. Therefore, bone marrow aspirate (or biopsy if adequate aspirate is not attainable) must be collected at screening so slides of bone marrow aspirate (and/or biopsy) and peripheral blood smear are available for both the local and the central pathology reviewers. A bone marrow biopsy can be collected in conjunction with an aspirate if it is standard institutional practice. Whenever a bone marrow sample is collected, a peripheral blood smear is to be prepared. In addition, a sample of the screening bone marrow aspirate is to be sent to the local or central cytogenetics laboratory (for sites without local analysis capability) for standard metaphase preparation and analysis of a minimum of 20 metaphase cells. A bone marrow biopsy can be used for cytogenetics testing if adequate aspirate is not attainable (note that specific handling of the biopsy is required for cytogenetics testing).

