### 6.2.1. Baseline

Unless noted otherwise for a particular assessment, results obtained just prior to the start of study treatment on Day 1 of Cycle 1 will serve as the baseline values. If not available, the most recent screening results prior to the start of study treatment on Day 1 of Cycle 1 will be considered the baseline values. Transfusions history includes the type, number of units, reason, and date of transfusions for the 8 weeks prior to the start of study treatment on Day 1 of Cycle 1. EORTC QLQ-30 and EQ-5D are to be completed prior to the start of study treatment on Day 1 of Cycle 1 and prior to interaction with study personnel.

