11.4.5. Fasting Lipid Panel

Fasting lipid panel includes total cholesterol, low-density lipoprotein cholesterol (LDL-C), high-density lipoprotein cholesterol (HDL-C), and triglycerides. Lipid profiles will be described by concentration of the lipids at scheduled visits. The proportion of subjects with clinically meaningful post-baseline increase in lipids will be summarized based on criteria presented in Table 6 below.

Table 6: Fasting Lipid Changes of Interest

Laboratory Test	Parameters for any value and the last value
LDL cholesterol	>ULN and >10% increase from BL
LDL-C/HDL-C ratio	>3.5 and >10% increase from BL

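### The SAP closes the BSC-only baseline at randomization, so when Cycle 1 Day 1 falls 1 to 3 days later the lipid baseline is missing and other baselines revert to screening values

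*SAP*

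**What the plan says.** SAP 5.1 (Reporting Conventions) has two baseline rules that matter here. The general rule, which covers AG-221, azacitidine, LDAC and IDAC, takes "the last non-missing value prior to or on the start of study treatment on Day 1 of Cycle 1". The BSC-only rule reads: "For subjects in the BSC only group, the baseline value will be defined as the last non-missing value on or prior to date of randomization". The same section adds that "for BSC only subjects, Day 1 is the randomization day".

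Protocol 6.2.1 has one rule for all subjects: "results obtained just prior to the start of study treatment on Day 1 of Cycle 1 will serve as the baseline values". Its fallback is the latest screening result: "If not available, the most recent screening results prior to the start of study treatment on Day 1 of Cycle 1". Neither sentence mentions BSC only.

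On timing, footnote d of Protocol Table 3 says: "The subject should start study treatment (ie, Day 1 of Cycle 1) within 3 days after randomization". Protocol 3.1.2 and 6.1 repeat the 3-day limit, also without a BSC exception. Under Protocol 6.1, screening evaluations "must be completed within 28 days prior to the start of study treatment".

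SAP 11.4.5 says: "The proportion of subjects with clinically meaningful post-baseline increase in lipids will be summarized". Table 6 in that section sets two criteria, one for LDL cholesterol and one for the LDL-C/HDL-C ratio. Each requires a rise of more than 10% from baseline as well as a threshold on the value itself.

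SAP Section 13, which lists changes from the protocol's statistical section, names only the transfusion-independence analysis.

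**The concern.** Where the Cycle 1 Day 1 visit comes after the day of randomization, the SAP rule shuts that visit's samples out of the BSC-only baseline, while the same visit supplies the baseline for AG-221. Two things follow.

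First, a test first drawn on Day 1 has no scheduled baseline at all in these subjects. Second, a test drawn at both screening and Day 1 gets an older baseline than in AG-221. Its Day 1 value is then counted as post-baseline, although the protocol treats it as the starting value.

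At stake is like-for-like reading of the summaries that use baseline: laboratory change, nadir and grade shifts (SAP 11.4), vital signs (11.5) and QTc increases (11.7). Baseline ECOG also defines an efficacy subgroup (10.4), and baseline ECOG, ANC and creatinine clearance define adverse-event subgroups (11.1). The mismatch is undiluted in the BSC-only column and partly carried into the pooled CCR column.

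**Working it through.** The plan states no figure on this point, so there is nothing to reproduce. The check is date arithmetic.

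**Inputs**
- R = randomization date. Cycle 1 Day 1 is R + L, with L = 0, 1, 2 or 3 days (Protocol Table 3, footnote d).
- The BSC-only baseline window closes at R (SAP 5.1).
- The window for drug-treated subjects closes at the start of treatment on Cycle 1 Day 1, that is R + L (SAP 5.1).
- A screening sample is taken S days before Cycle 1 Day 1, with S at most 28 (Protocol 6.1).
- Hematology, chemistry, ECG, vital signs and ECOG are marked at both screening and Day 1 in Protocol Table 3.
- The lipid panel and cardiac markers have blank screening cells in Table 3 and are absent from the screening laboratory list in Protocol 6.1. Their first scheduled draw is Cycle 1 Day 1.

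**Rule for the Day 1 sample.** It enters the BSC-only baseline only if R + L ≤ R, which requires L = 0.

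**Rule for the fallback.** If L ≥ 1, the BSC-only baseline is the last screening value dated on or before R. Its age at Cycle 1 Day 1 is S, with L ≤ S ≤ 28.

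| Lag L (days) | Day 1 sample counts as BSC-only baseline? | Scheduled lipid baseline, BSC-only | Age of other baselines at Day 1, BSC-only | Age in AG-221 with a Day 1 sample |
|---|---|---|---|---|
| 0 | yes | yes | 0 days | 0 days |
| 1 | no | none | 1 to 28 days | 0 days |
| 2 | no | none | 2 to 28 days | 0 days |
| 3 | no | none | 3 to 28 days | 0 days |

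**Which analyses need the missing value.** Both Table 6 lipid flags contain a percentage change from baseline, so they cannot be derived at L = 1 to 3. The cardiac-marker summary in SAP 11.4.6 counts values above the upper limit of normal and needs no baseline. Tests with a screening value remain derivable, but from an older reference.

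**Where the Day 1 value goes instead.** SAP Section 11 starts the BSC-only safety treatment period at randomization. At L = 1 to 3 the Day 1 value therefore lies inside that period and can supply the nadir, the worst grade or the maximum QTc. In AG-221 the value from the same visit is the baseline.

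**After the change proposed below.** The BSC-only window closes at R + L, so the Day 1 sample qualifies at every L from 0 to 3. Where it was taken, the lipid baseline exists and every baseline has age 0, as in AG-221.

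**The case against.** The best defence is that the rule is a coherent convention. BSC only has no first dose, and Protocol 9.2.3 accepts that supportive care may consist of products given when the need arises. The protocol never says which event starts treatment for these subjects, and Section 9 leaves final methods to the SAP. The SAP then anchors BSC only at randomization throughout: Day 1 and cycles (5.1), start of treatment (8.4), duration (9.1) and the safety period (Section 11). On that reading the SAP follows the protocol's principle, and silence in Section 13 is a small matter. Moving only the baseline would also put it up to 3 days inside a treatment period that has already begun.

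Much of this stands. Randomization is a reasonable time origin for BSC only, and the fix has to deal with the overlap. But naming the randomization date Day 1 does not move the visit at which blood is drawn, and it does not create a lipid sample before that visit.

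A same-day baseline is also not guaranteed in AG-221, since a subject without a Day 1 result falls back to screening there too. And 28 days is the outer limit of the screening window, not a typical age.

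A reader might infer more than the documents support:
- **That BSC-only subjects drop out of the lipid table altogether.** Only those with a lag of 1 to 3 days lose the flags; same-day starts are unaffected.
- **That the rule makes CCR look worse.** This needs a steady decline between screening and Day 1. Transfusions and hydroxyurea are permitted, so counts can move either way, and nothing in the documents fixes a direction for lipids, chemistry or QTc.
- **That troponin reporting is damaged.** The summary specified for it uses only the upper limit of normal.
- **That a number of affected subjects can be stated.** An assumed BSC-only share of 10% to 40% of the 158 CCR subjects gives 0.10 × 158 ≈ 16 to 0.40 × 158 ≈ 63. That share is not in the documents, and the count also presumes that every such subject has a lag of at least 1 day.

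**Conclusion.** The conflict between SAP 5.1 and Protocol 6.2.1 is real and worth correcting, within limits. For BSC-only subjects whose Cycle 1 Day 1 is 1 to 3 days after randomization, the two Table 6 lipid flags cannot be derived. For the same subjects, hematology, chemistry, ECG, vital signs and ECOG take a screening baseline up to 28 days old, and the Day 1 value is treated as post-baseline.

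This rests on two assumptions: BSC-only subjects attend Cycle 1 Day 1 on the schedule that applies to everyone else, and no unscheduled lipid sample was taken on or before randomization.

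The consequence is confined to safety, change-from-baseline and baseline-subgroup summaries. The primary OS test runs from randomization on the ITT population and uses none of these baselines. Neither the number of subjects affected nor the direction of any distortion can be computed from the documents. The point does not depend on either: the lipid flags are underivable, and the reference visit differs between groups, whichever way the values move.

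**What to change.** In SAP 5.1, define the BSC-only baseline as the last non-missing value on or before the Cycle 1 Day 1 visit date, using the randomization date only where there was no such visit. State that this value (and, by the same logic, any earlier one) is excluded from on-treatment nadir, worst-grade and maximum summaries. Leave randomization as Day 1 for BSC-only adverse-event, exposure and cycle calculations.

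If the sponsor prefers the present rule, it should be listed and justified in SAP Section 13, with a statement that the lipid flags are not derivable for BSC-only subjects with a lag of 1 to 3 days.

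The cost is two or three sentences and a revised baseline flag in the analysis datasets. No new data are needed, and the change can be made before the final database lock. The one drawback is that the SAP needs an explicit exception, because baseline may then fall up to 3 days after SAP Day 1 for BSC-only subjects.
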